An Open-label Study to Investigate the Efficacy and Tolerability of Aczone Gel, 7.5% in the Treatment of Acne Vulgaris in Men and Women With Skin of Color

[name]

NCT03681470

Document Date: Feb 7, 2022

Protocol Document for 17-01277
Principal Investigator: [name].
Mount Sinai

Brief Summary of Research

Acne vulgaris is a common skin disease characterized by inflammatory papules, pustules, and comedones that is prevalent in men and women of color. Research has demonstrated that Aczone[®] (dapson) gel, 7.5% used once daily is effective, safe, and well-tolerated for the treatment of acne in both men and women; however, no data is available regarding its efficacy and safety in skin of color (SOC). The current study aims to investigate the therapeutic impact of Aczone gel 7.5% in SOC males and females ages 18 and older with acne vulgaris. The study will also evaluate the impact of Aczone[®] gel on hyperpigmentation and PIH of the face.

Objectives

The purpose of this study is to evaluate the safety and efficacy of Aczone[®] gel, 7.5% administered once daily for 24 weeks in males or females with skin of color (SOC), defined as Fitzpatrick Skin Types IV, V, or VI, for the treatment of facial acne vulgaris.

Background

Acne vulgaris is a common skin disease characterized by inflammatory papules, pustules, and comedones that is prevalent in men and women of color. In fact, acne is the most common dermatologic diagnosis made in SOC populations (1). Although individuals of all skin types can develop acne vulgaris, there are important differences in darker skin types that are important to consider when choosing an optimal treatment (2).

From a diagnosis standpoint, acne in women of color is more likely to present on the cheek area, as opposed to a chin and cheek predominance in white women (2). Complications from acne are of great concern in this population, as women of color are more likely to develop keloids, hypertrophic scars, and post-inflammatory hyperpigmentation (PIH) as a result of acne lesions (3). PIH may last for weeks to months and, in many cases, is more troublesome to patients than the acne itself (2). Overall, facial acne and its sequelae have a greater impact on perception of appearance, negative emotions, and social functioning in women of color than white women (2).

Dapsone is a sulfone compound with anti-inflammatory properties that has been shown to be effective in the treatment of acne vulgaris in SOC (4). Aczone[®] (dapson) gel, 5% administered twice daily has been associated with significant improvement in overall acne severity, acne signs, and impact on quality of life in women of color (4). Two phase III trials of a newer formulation of Aczone[®] (dapson) gel, 7.5% used once daily demonstrated that this product is effective, safe, and well-tolerated for the treatment of acne in both men and women (5); however, no data is available regarding its efficacy and safety in SOC.

Further, some investigators of the phase IV study on the safety and efficacy of dapson gel 5% in SOC anecdotally reported improvement in hyperpigmentation over 12 weeks, although this was not a planned efficacy outcome (4). Further research is needed on the potential effects of dapson gel on hyperpigmentation and PIH in SOC.

The current study will investigate the therapeutic impact of Aczone gel 7.5% in SOC males and females ages 18 and older with acne vulgaris. The study will also evaluate the impact of Aczone gel on post-inflammatory hyperpigmentation using the Postacne Hyperpigmentation Index (PAHPI) and mexameter-measured melanin index (MI).

Setting of the Human Research

All research activity will take place at Mount Sinai Department of Dermatology.

Resources Available to Conduct the Human Research

The research team consists of the Principal Investigator, Sub-Investigator and Research Coordinator. We do not foresee any difficulties in recruiting the suggested number of patients for this research study.

All members of the study team have several years of research experience and have all completed the required trainings and certifications mandated by our IRB.

All research team members have read and understand the protocol and all study related procedures.

Study Design

a) Recruitment Methods

Subjects will be recruited from the dermatology faculty practices and the dermatology resident clinics in the Mount Sinai Health System. Once approved by the Sponsor, we will use IRB approved flyers, online advertisements (including social media postings and clinical trials listing services) as well as questionnaires and phone scripts.

b) Inclusion and Exclusion Criteria

Inclusion:

1. Provide written, signed and dated informed consent prior to initiating any study-related activities.
2. Male or female subjects who are ≥ 18 years of age
3. Subjects with Fitzpatrick Skin Type IV, V, or VI
4. Subjects with moderate to severe acne as defined by investigator-assessed Global Acne Assessment Score (GAAS) of 3 or 4 at screening
5. Facial acne vulgaris with 20 to 50 (inclusive) inflammatory lesions and 30 to 100 (inclusive) noninflammatory lesion
6. Stable non-progressive or regressive acne vulgaris in the investigator's opinion

7. Females of childbearing potential (FCBP) must have a negative pregnancy test at Screening and Baseline. A female is considered not to be of childbearing potential if she is post-menopausal with at least 12 consecutive months of amenorrhea or has undergone surgical sterilization. While on investigational product and for at least 28 days after taking the last dose of investigational product, FCBP who engage in activity in which conception is possible must use one of the approved contraceptive options described below:

Option 1: Any one of the following highly effective methods: hormonal contraception (oral, injection, implant, transdermal patch, vaginal ring); intrauterine device (IUD); tubal ligation; or partner's vasectomy;

OR

Option 2: Male or female condom (latex condom or nonlatex condom NOT made out of natural [animal] membrane [for example, polyurethane]); PLUS one additional barrier method: (a) diaphragm with spermicide; (b) cervical cap with spermicide; or (c) contraceptive sponge with spermicide.

8. Must be in general good as judged by the Investigator
9. Subject is willing to avoid excessive or prolonged exposure of the treated skin to ultraviolet light (i.e. sunlight, tanning beds) throughout the study
10. Subject is willing to follow study instructions and complete study assessments without assistance and is likely to complete all required visits

Exclusion:

1. Diagnosis of other dermatologic diagnosis that, in the opinion of the investigator, would interfere with diagnosis, examination, or treatment of the studied condition (i.e. psoriasis, atopic dermatitis, lupus, dermatomyositis, seborrheic dermatitis, perioral dermatitis, etc.)
2. Subjects with severe cystic acne, acne conglobate, acne fulminans, or secondary acne (chloracne or drug-induced acne)
3. Uncontrolled systemic disease(s) that, in the opinion of the investigator, would put the patient at significant risk if enrolled in the study or would interfere with subject's participation in the study
4. Subjects with a history of clinically significant hemolysis, anemia, or enteritis (regional enteritis, ulcerative colitis, pseudomembranous colitis, antibiotic-associated colitis)
5. Subjects with allergy or sensitivity to the study drug or its components
6. Subjects who have not complied with the proper wash-out periods:
 - a. Topical anti-inflammatory medications, salicylic acid, corticosteroids, antibiotics, antibacterials, peroxide-containing products, or retinoids within 2 weeks of baseline
 - b. Systemic antibiotics, corticosteroids, antimalarials or oral dapsone within 4 weeks of baseline

- c. Other anti-acne medication, including isotretinoin or spironolactone, within 6 months of baseline
 - d. Chemical peels or other facial acne procedures (laser therapy, light therapy) within 3 months of baseline
 - e. Treatment with botulinum toxin of any serotype in the face within 6 months of baseline
 - f. Estrogens/Birth control pills must have been started ≥ 90 days prior to baseline and use must be continued during the study without alteration or discontinuation.
7. Pregnant or breastfeeding.
 8. Subjects with evidence of alcohol or substance abuse.
 9. Use of any investigational drug within 4 weeks prior to randomization, or 5 pharmacokinetic/pharmacodynamic half-lives, if known (whichever is longer).

c) Number of Subjects

Up to 40 subjects with acne vulgaris will be screened with a goal of 20 total subjects randomized. All 20 randomized subjects are expected to complete all study procedures. Individuals who provide informed consent and fail to meet all of the inclusion and exclusion criteria during the initial evaluation will be considered a “screening failure.”

d) Study Timelines

The study will consist of 6 in-person visits and one phone visit (7 total visits) over up to 28 weeks (4 week screening period plus 24 weeks enrolled in study). Study visits will be conducted at Screening (Visit 1), Baseline (Visit 2, Week 0), Week 4 (Visit 3), Week 8 phone visit (Visit 4), Week 12 (Visit 5), Week 18 (Visit 6), Week 24 (Visit 7).

Enrollment will occur over a 24-36 month period from January 2018 to December 2020. The study is anticipated to be completed by December 2021.

e) Endpoints

Primary Endpoint:

1. Mean change from baseline to week 12 in Global Acne Assessment Score (GAAS)

Secondary Endpoints:

1. Change from baseline in Global Acne Assessment Score (GAAS) at week 4, 18, and 24.
2. Change from baseline in Post Acne Hyperpigmentation Index (PAHPI) at weeks 12, 18, and 24.
3. Change from baseline in Melanin Index (MI) of target lesion at weeks 12, 18, and 24
4. Change from baseline in the proportion of subjects with score of 0 or 1 on ASIS “dark spot” score at weeks 4, 12, 18, and 24.
5. Proportion of subjects with GAAS of 0 (none) or 1 (minimal) at weeks 4, 12, 18, and 24

6. Percent change from baseline in all lesion counts (inflammatory, noninflammatory, and total) at weeks 4, 12, 18, and 24.

f) Procedures Involved in the Human Research

This is a single-center, single-group, open-label study using Aczone® (dapson) gel 7.5%. All subjects will receive the study medication. Aczone® gel is an off-white to yellow gel with suspended particles. It is supplied in an airless pump containing a polypropylene bottle with a high density polyethylene piston. It will be dispensed as a 60g pump.

Subject will apply Aczone® once daily to the entire face. Study drug must not be applied to other areas of the body, including the upper chest, upper back or shoulders.

Prior to the start of the study, potential subjects will be given an IRB-approved Informed Consent Document (ICD) containing a Health Insurance Portability and Accountability Act (HIPAA) disclosure agreement to read, understand, and sign. All questions about the study should be answered to the satisfaction of the candidate subject. They will have all of their study-related questions answered by the PI or designee, and if they agree to participate, the subject will sign two original copies of the ICD. The subjects will retain one original copy and one original copy will be kept in the study file. The subjects who sign an ICD will be assigned a screening number.

After providing informed consent, subjects will be assessed for study eligibility at the Screening visit (day -28 to day -1), which includes review of medical history and concomitant, acne lesion counting and severity ratings, and serum pregnancy test (if applicable). The PI or a medically qualified designee must review this information (i.e. medical history, concomitant medication, and eligibility review) for each subject to confirm their eligibility before enrollment. A total of 20 subjects who meet eligibility criteria will undergo Baseline / Day 0 assessments. Subjects will return for visits at weeks 4, 12, 18, and 24. There will be a phone visit at week 8.

Study Assessments and Efficacy Measures:

Global Acne Assessment Score (GAAS):

The subject's acne severity will be assessed by the investigator using a 5-point GAAS at screening, baseline, and weeks 4, 12, 18, 24.

Grade	Description
0	None No evidence of facial acne vulgaris
1	Minimal Few noninflammatory lesions are present; a few inflammatory lesions (papules/pustules) may be present; no nodulo-cystic lesions present
2	Mild Several to many noninflammatory lesions are present; a few inflammatory lesions are present; no nodulo-cystic lesions present.
3	Moderate Many noninflammatory and inflammatory lesions are present; no nodulo-cystic lesions are present.
4	Severe Significant degree of inflammatory disease; papules and pustules are a predominant feature; a few nodulo-cystic lesions are present (no more than 2)

Lesion Counts:

The lesion counts, including inflammatory and non-inflammatory lesions, will be performed at screening, baseline, and weeks 4, 12, 18, and 24. Inflammatory lesions (papules, pustules, nodules/cysts) and

noninflammatory lesions (open comedone, closed comedone) will be counted individually. The sum of the inflammatory lesion counts and non-inflammatory lesion counts will be totaled.

ASIS ®:

Acne Symptom and Impact Scale (ASIS ®) will be given to subjects' for completion at baseline and weeks 4, 12, 18, and 24. The ASIS ® contains 9 items assessing symptom severity and 8 items assessing the psychosocial impact of acne vulgaris (6). High scores on the ASIS® indicate the presence of more severe symptoms, whereas higher scores on the ASIS indicate better outcomes on acne health-related quality of life.

PAPHI:

The postacne hyperpigmentation index (PAHPI) has been shown to be a reliable and valid score measuring post-inflammatory hyperpigmentation from acne (7). PAHPI will be scored using the following formula:

Total PAHPI = S + I + N

PAHPI Score can range from 6-22.

Lesion Size (S)

Weighted Score (S)	Median Lesion size
2	<3mm
4	3-6mm
6	7-10mm
8	>10mm

Lesion Intensity (I)

Weighted Score (I)	Median Lesion Intensity
3	Slightly darker than surrounding skin
6	Moderately darker than surrounding skin
9	Significantly darker than surrounding skin

Lesion Number (N)

Weighted Score (N)	Number of Lesions
1	1-15
2	16-30
3	31-45

4	46-60
---	-------

5	>60
---	-----

Melanin Index:

A narrowband reflectance spectrophotometer (mexameter MX-16) will be used to measure the degree of pigmentation of involved and adjacent uninvolved skin of one representative facial PIH lesion (8).

The mexameter contains 16 light emitting diodes arranged circularly that emit light at wavelengths of 568nm (green), 660nm (red), and 880nm (near infrared). The machine then measures the amount of light absorbed and reflected by the skin to measure the melanin content (melanin index or “M” – red and near infrared light) and hemoglobin content (erythema index or “E” – green and right light).

One target lesion will be chosen by the investigator, which will be the darkest spot involved by post-inflammatory hyperpigmentation without evidence of active acne lesion (inflammatory or non-inflammatory lesion). The target lesion must be on the face and easily accessible with the mexameter probe. The probe will be applied to the target lesion on the skin with light, constant pressure. Both the “M” and “E” indices will be recorded. The location of the target site will be recorded using distance from anatomic landmarks.

Skin Phototype Assessment:

At screening, Fitzpatrick skin type (FST) will be rated by the investigator:

- I: always burns, never tans (very pale)
- II: always burns, tans minimally (pale)
- III: burns moderately, tans gradually (light brown)
- IV: burns minimally, always tans well (moderate brown)
- V: rarely burns, tans profusely (dark brown)
- VI: never burns, deeply pigmented (very dark brown)

Photography:

Standardized photographs will be taken by study personnel at baseline and weeks 12, 18, and 24 using standardized cameras and photographic equipment.

Subject Safety Measures:

The following safety measures will be collected:

- Adverse events
 - o The investigator will question the subject at all scheduled visits and one phone visit to determine whether adverse events were experienced since the prior visit. The adverse event and all applicable information (date of onset, date of stop, duration, outcome, severity, relationship to study drug, action or treatment required) will be obtained and recorded on the source documents and adverse event CRF.
- Local tolerability assessments
 - o Investigator will ask subject to rate subjective burning/stinging using the following scale: 0 = absent (normal, no discomfort), 1 = trace (an awareness, but no discomfort and no intervention required), 2 = mild (noticeable discomfort causing intermittent awareness), 3 = moderate (noticeable discomfort causing continuous awareness), 4 = marked (definite discomfort causing continuous awareness, interfering occasionally with normal daily activities), 5 = severe (definite, continuous discomfort interfering with normal daily activities)
 - o Investigator will rate erythema, dryness, peeling, and oiliness using the following scale:

Score	Erythema	Dryness	Peeling	Oiliness
0=absent	No redness	None	Smooth	Normal

1=trace	Faint red or pink coloration, barely perceptible	Barely perceptible dryness by palpation with no accentuation of skin markings, skin desquamation (flakes) or fissure formation	Fine peeling, barely perceptible	Mild and localized
2=mild	Light red or pink coloration	Easily perceptible dryness by palpation with accentuation of skin markings but no skin desquamation (flakes) or fissure formation	Slight peeling	Mild and diffuse
3=moderate	Medium red coloration	Easily noted dryness with accentuation of skin markings and skin desquamation (small flakes) but no fissure formation	Definitely noticeable peeling	Moderate and diffuse
4=severe	Beet red coloration	Easily noted dryness with accentuation of skin marking, desquamation (large flakes) and/or fissure formation	Extensive peeling	Prominent and dense

- Urine pregnancy tests at screening, baseline, and weeks 4, 12, 18, and 24.
- Concomitant medications and procedures

Drug Dispensation:

Drug will be dispensed at the baseline visit and the first dose of study drug will occur during this visit in the office under the investigator’s supervision. The subject will gently wash the face and pat it dry. Then the subject will apply a pea-sized amount in a thin layer to the entire face and rub in the product gently and completely until there is no visible mass of gel observed on the face. All subjects will be provided a subject application instruction sheet. Adherence to the instructions will be assessed at subsequent visits and subjects will be re-trained at scheduled visits if necessary. Additional study drug will be dispensed every 4-8 weeks as needed.

Visit Schedule:

Screening:

- Informed Consent
- Demographics
- Inclusion/Exclusion
- Medical History
- Concomitant medications and procedures
- Skin phototype assessment (Fitzpatrick Skin Type)
- Lesion Counting
- Global Acne Assessment Score (GAAS)
- Adverse events
- Urine pregnancy

Baseline

- Inclusion/Exclusion
- Adverse events
- Concomitant medications and procedures
- Lesion Counting
- Melanin index

- GAAS
- Post Acne Hyperpigmentation Index (PAHPI)
- ASIS dark spot score
- Local tolerability assessment
- Photography
- Urine pregnancy
- Product dispensation/return

Week 4 –

- Adverse events
- Concomitant medications and procedures
- Lesion Count
- GAAS
- ASIS dark spot score
- Local tolerability assessment
- Pregnancy test
- Product dispensation/return

Week 8 Phone Visit –

- Adverse events
- Concomitant medications and procedures

Week 12 –

- Adverse events
- Concomitant medications and procedures
- Lesion Counting
- GAAS
- PAHPI
- ASIS dark spot score
- MI
- Photography
- Local tolerability assessment
- Product dispensation/return
- Urine pregnancy test

Week 18 –

- Adverse events
- Concomitant medications and procedures
- Lesion Counting
- GAAS
- PAHPI
- ASIS dark spot score
- MI
- Photography
- Local tolerability assessment
- Product dispensation/return
- Urine Pregnancy test

Week 24 –

- Adverse events
- Concomitant medications and procedures
- Lesion Counting
- GAAS
- PAHPI
- ASIS dark spot score
- MI
- Photography
- Local tolerability assessment
- Product return
- Urine Pregnancy test

Table 1: Assessment Schedule

Visit	1	2	3	4	5	6	7
Week	-4 to BL	0 (BL)	4	8 phone	12	18	24
Visit Window (days)			±3	±3	±3	±3	±3
Assessment							
Informed Consent	X						
Demographics	X						
Inclusion/Exclusion	X	X					
Medical History	X						
Fitzpatrick Skin Type	X						
AE/SAE assessment	X	X	X	X	X	X	X
Concomitant medications	X	X	X	X	X	X	X
Concomitant procedures	X	X	X	X	X	X	X
Photography		X			X	X	X
Urine Pregnancy Test	X	X	X		X	X	X
Lesion Count	X	X	X		X	X	X
GAAS	X	X	X		X	X	X
ASIS ®		X	X		X	X	X
PAHPI		X			X	X	X
Mexameter – Melanin Index		X			X	X	X
Local tolerability		X	X		X	X	X
Study Drug Dispensation and Return		X	X		X	X	X

g) Specimen Banking

Not applicable.

h) Data Management and Confidentiality

As used in this protocol, the term case report form (CRF) should be understood to refer to either a paper form or an electronic data record or both, depending on the data collection method used in this trial. All subject source documents are the site's subject records and are to be maintained at the study site. These source documents must be attributable, legible, contemporaneous, original, and accurate.

A CRF/source document is required and should be completed for each included subject. It is the PI's responsibility to ensure completion and to review and approve all CRFs/source documents. These must be signed by the PI or by an authorized staff member. These signatures serve to attest that the information contained on the CRFs/source documents is true. At all times, the PI has final personal responsibility for the accuracy and authenticity of all clinical and laboratory data entered on the CRFs/source documents. SAE forms and pregnancy notification forms will be provided by the Sponsor.

Good documentation practices should be used on all study documentation. The clinical study will be performed in accordance with the protocol, applicable standard operating procedures (SOPs), the International Conference on Harmonization Good Clinical Practice (ICH GCP) guidelines, and applicable local regulatory requirements and laws.

The Sponsor requires that all records (e.g., ICFs, documents, test article dispensing record, etc.) which support CRFs/source documentation of this study must be retained in the files of the responsible investigator for a period of 2 years from the time the final report is issued.

If the investigator relocates, retires, or for any reason withdraws from the trial, the Sponsor should be prospectively notified. The study records must be transferred to an acceptable designee, such as another investigator, another institution, or to the Sponsor. The investigator must obtain Sponsor's written permission before disposing of any records, even if retention requirements have been met. The Sponsor must be notified in writing of the name and address of the new custodian prior to re-assignment/transfer.

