Study drug is stored in a combination-locked room accessible only by clinical trials personnel. All study materials should be stored at room temperature (59°-77°F), and the Site is responsible for maintaining temperature logs. All study products received and dispensed will be inventoried and accounted for throughout the study. The investigator must maintain adequate records documenting the receipt, use, loss, or other disposition of the products on the Product Accountability Log. The log must identify the investigational product and account for its disposition by subject, including specific dates and quantities dispensed and returned. The log must be signed by the individual who dispensed/retrieved the study product and copies must be provided to the sponsor for inclusion in the Trial Master File.

At the completion of the study, all units of product dispensed (whether empty or containing unused product) must be collected by the Site and returned, along with un-dispensed product, to the Sponsor. Any container not returned by the Site must be accounted for in writing.

k) Statistical Analysis Plan

The adverse events will be tabulated according to their date of onset, duration, severity and relationship to the treatment. We will build Clopper-Pearson 90% confidence intervals for the proportion of adverse events considering their aggregation and stratification (e.g., by severity).

Sample Size Considerations

A sample size of $n=20$ subjects allows $>90\%$ power at 5% significance level for a two-sided paired t-test to detect at week 12 a minimum change in GAAS from baseline of 1 grade point. This calculation was performed in G*Power and it assumes a mean GAAS of 3.5 at baseline and a maximal standard deviation of 0.513.

Analysis of primary Endpoint

The primary analysis will apply a two-sided paired t-test to assess the significance of the change in GAAS from baseline to week 12. However, GAAS is an ordinal measurement and, for this reason, we will also apply a Generalized Linear Mixed-effects Model (GLMM) to assess the significance of the changes in GAAS after including potential covariates.

Analysis of secondary Endpoints

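### Inclusion 6 is ambiguous and, on its ordinary reading, admits improving acne but excludes worsening acne, in a single-group study that tests GAAS change against zero

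*Combined protocol and SAP*

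**What the plan says.** Study Design, section b, Inclusion 6 admits subjects with "Stable non-progressive or regressive acne vulgaris in the investigator's opinion". It gives no definition, look-back period or measured threshold. The neighbouring criteria set severity: an "investigator-assessed Global Acne Assessment Score (GAAS) of 3 or 4 at screening" and "Facial acne vulgaris with 20 to 50 (inclusive) inflammatory lesions and 30 to 100 (inclusive) noninflammatory lesion".

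The Objectives section states the aim: "The purpose of this study is to evaluate the safety and efficacy of Aczone[®] gel, 7.5% administered once daily for 24 weeks". Section f gives the design: "This is a single-center, single-group, open-label study using Aczone® (dapson) gel 7.5%. All subjects will receive the study medication". Section e makes the mean GAAS change from baseline to week 12 the primary endpoint. In section k the primary analysis is a "two-sided paired t-test to assess the significance of the change in GAAS from baseline to week 12", supplemented by a mixed model with covariates that are not named. For the ordinal secondary endpoints, GAAS at other visits among them, section k treats a high count off the diagonal of the baseline-by-visit table as evidence of a treatment effect.

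Table 1 schedules GAAS and lesion counts at both screening and baseline. No planned analysis uses the change between those two visits.

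**The concern.** With no control group, a mean change different from zero indicates a drug effect only if the average untreated change would be about zero. A criterion that removes subjects who are getting worse and keeps those who are getting better works against that condition, and in the direction that favours the gel. Fluctuation and regression to the mean are limits of every single-group study. This criterion is a separate choice that can add to them, and it can be avoided. At stake is whether a fall in GAAS may be reported as efficacy.

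**Working it through.** **1. The two readings of Inclusion 6**

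| Course before entry | Reading A: (stable, non-progressive) or (regressive) | Reading B: stable, i.e. neither progressive nor regressive |
|---|---|---|
| Worsening | excluded | excluded |
| Unchanged | admitted | admitted |
| Improving | admitted | excluded |

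Reading A is the ordinary one: the prefix *non-* is attached to one adjective only, and *or* introduces an alternative. Reading B is the one that keeps the word *stable* coherent. The text does not settle the matter, and each decision is left to the investigator's opinion.

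**2. What the primary test can separate**

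Let d be week-12 minus baseline GAAS. The test is t = mean(d) / (SD(d)/√n) with n − 1 degrees of freedom. The expected value of d is the drug effect plus the untreated change. All subjects start the gel at baseline, so time in study and time on drug coincide. Neither the t-test nor a mixed model with covariates can split the two parts.

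**3. Whether other provisions cancel the one-sided filter**

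- *GAAS and lesion-count ranges.* They limit how far an improving subject can have improved and still enter. They do not exclude improving subjects, and the GAAS criterion names screening only.
- *Eligibility review repeated at baseline.* It applies the same wording again.
- *Washouts (Exclusion 6).* They limit carry-over from earlier therapy. They do not address acne improving by itself.
- *External reference, expected untreated change or pre-baseline trend.* None is stated.

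**4. The plan's own figure**

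Inputs from Sample Size Considerations: n = 20, change of 1 grade, SD 0.513, two-sided 5%.

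Noncentrality = 1 / 0.513 × √20 = 8.72 with 19 degrees of freedom. Power is above 99.99%, which agrees with the stated power of more than 90%.

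An SD of 0.513 is also the SD of ten scores of 3 and ten of 4: √(10 × 10 / (20 × 19)) = 0.513. It may therefore describe the baseline scores rather than the change. If baseline and week 12 had that SD and were uncorrelated, the SD of change would be 0.513 × √2 = 0.725.

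**5. How small a mean fall is significant**

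Threshold = t(0.975, 19) × SD / √20, with t(0.975, 19) = 2.093.

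- SD 0.513: 0.24 grade
- SD 0.725: 0.34 grade
- SD 1.0 (assumed): 0.47 grade

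At the plan's SD the threshold is about a quarter of the 1-grade planning effect.

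**6. In whole grades**

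If k of 20 subjects fall one grade and the rest do not change, mean = −k/20 and SD = √(k(20 − k) / (20 × 19)).

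| k | Mean | SD | t | p |
|---|---|---|---|---|
| 3 | −0.15 | 0.366 | −1.83 | 0.083 |
| 4 | −0.20 | 0.410 | −2.18 | 0.042 |
| 5 | −0.25 | 0.444 | −2.52 | 0.021 |

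The row for k = 4 depends on the other 16 not moving at all. At SD 0.513 a mean fall of 0.20 gives t = 0.20 × √20 / 0.513 = 1.74 in size, below 2.093; a fall of 0.25 gives 2.18, above it. Steps 5 and 6 hold whatever causes the falls, so they describe the uncontrolled design and not the contribution of Inclusion 6.

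**The case against.** The strongest reply has three parts.

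*The wording may already be symmetric.* Reading B is possible, and then nobody with improving acne is admitted. This stands as to intent. It does not remove the need to reword, because a site can follow either reading.

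*The figures belong to the design, not to the criterion.* This stands. A reader might infer that Inclusion 6 by itself produces a false-positive rate of 30% to 41%. Those rates do come out of a simulation with no drug effect in which 20% of subjects fall one grade and the rest move up or down one grade with probability 10% or 5% each way; with nobody regressing, the rates of declared improvement are 2.3% and 0.6%. But the 20% is an assumed share of regression from any source. The relevant quantity is the extra share let in by the words *or regressive*, and the documents give no figure for it. They also do not show that improvement before entry continues for 12 weeks. So they do not support the claim that spontaneous improvement will be counted as efficacy to any stated extent.

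*Rewording may come too late.* The document is dated February 2022, while section d planned enrolment to end in December 2020 and completion by December 2021. If that timetable was kept, a new criterion changes nobody who entered. The limit on the conclusion would still apply.

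**Conclusion.** The point holds as one of ambiguous wording with a directional risk. On the ordinary reading the filter is one-sided, and nothing else in the plan offsets it. The direction is favourable to the gel, on the assumption that improvement before entry carries on to some extent afterwards. The size of the bias cannot be calculated from the documents: the number of subjects admitted while improving and their untreated course are both unknown. The sensitivity of the test shows only that a modest fall from any cause would be enough for significance. It does not show that an inert gel would succeed in this trial. Rewording would reduce the bias without removing it, since natural fluctuation and regression to the mean remain in any single-group study.

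**What to change.** 1. Reword Inclusion 6 to: *Stable acne vulgaris, neither progressing nor regressing, in the investigator's opinion*, and say that this is judged with the GAAS and lesion counts already taken at screening and baseline.

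2. Do not turn this into a rule that the GAAS grade must be identical at both visits. Under section f screening can be as late as day −1, when two equal grades say nothing about trend, and slow regression can pass on a five-grade scale. The rule would also make the screening-to-baseline GAAS change zero for every enrolled subject by construction.

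3. Add a descriptive table of the screening-to-baseline change in GAAS and lesion counts for all subjects with both visits, with the interval length and any treatment stopped for washout. Do not present it as a clean untreated reference. Washouts run back from baseline (for example 2 weeks for topicals), while screening may be at day −28, so a subject may stop treatment between the two visits.

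4. State in the analysis plan and report that change from baseline cannot be attributed to the gel alone.

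Cost: one amended criterion, one table and one sentence, with no new visit or assessment. There may be a few more screen failures; the number is not known, and section c allows up to 40 screened for 20 enrolled. If enrolment has closed, only items 3 and 4 apply.
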